11.3.1 Natural history growth rates

Based on two assessments of GA growth measured with Cirrus OCT,^{32,33} we assume that in the absence of treatment average square root area lesion growth is 0.33mm/year (mean of 0.28mm/year³³ and 0.37mm/year³²) and the standard deviation of annual square root area growth is 0.21mm/year.³²

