## Statistical Analysis Plan

---

0.2mm/year and a 2-sided test at the 10% level of significance.

Assuming a 15-20% loss to follow-up, a total sample size of 240 subjects (AM=80, AEOM=80, SM=40 and SEOM=40) will be required to obtain 201 evaluable subjects (i.e. subjects who complete the study).

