### 6. GENERAL ASPECTS FOR STATISTICAL ANALYSIS

#### 6.1. GENERAL METHODS

All statistical tests will be 2-sided at the 0.1 level of significance. To understand the clinical significance of the estimated treatment effects and to aid interpretation of the formal hypothesis testing 2-sided 95% CI will also be provided. There will not be any adjustments for multiple comparisons.

For all independent ophthalmic assessments (performed by DARC laboratory), if assessments by only two independent readers are available, then the mean of the 2 readings will be used in the calculation of summary statistics. If assessments by three independent readers are available, then the median of the three readings will be used for the summary calculations.

Continuous variables will be summarized using the number of non-missing observations (n), mean, standard deviation (SD), median, minimum, and maximum. Geometric mean and coefficient of variation (CV) will be included for PK parameters, where appropriate. Categorical variables will be summarized using frequencies and percentages. Unless stated otherwise, for all percentages, the number of subjects in the analysis population for the treatment group will be the denominator.

Unless otherwise specified, the estimated mean and median for a set of values should be printed out to 1 more decimal place than the original values, and standard deviations should be printed out to 2 more decimal places than the original values. The minimum and maximum should report the same number of decimal places as the original values. Percentages will be displayed with 1 decimal place; except percentages will not be presented when the count is zero and 100% will be presented as an integer.

Unless stated otherwise, baseline will be taken as the last available non-missing assessment prior to first study drug administration.

Subjects can discontinue treatment but remain in the study for follow-up. All assessments will be included in summary tables or analyses unless stated otherwise.

For all summary tables, data will be presented by treatment group and by pooled sham and pooled APL-2. For summaries by-visit pooled sham and pooled APL-2 will only be presented for the bi-monthly visits. The treatment group labels for summary tables will be:

- APL-2 Monthly
- APL-2 EOM
- APL-2 Pooled
- Sham Monthly
- Sham EOM
- Sham Pooled

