#### **8.1. PRIMARY EFFICACY ENDPOINT AND ANALYSIS**

The primary endpoint is the change from baseline in square root area for GA lesion at Month 12 as measured by FAF. Baseline will be taken as the last available non-missing assessment prior to first study drug administration, this should be the screening assessment for the primary endpoint.

The change from baseline in square root area for GA lesion at Month 2, 6 and 12 will be analysed for the MITT population with a MMRM. The model will include the fixed effects of treatment (3 groups: AM, AEOM and Sham), baseline square root area for GA lesion, visit (2, 6 and 12 months), treatment by visit interaction, visit by baseline interaction and treatment by baseline interaction. An unstructured covariance structure will be used to model the within subject error. The Kenward-Rogers approximation will be used to estimate the denominator degrees of freedom. If the treatment by baseline interaction is not significant at the 10% level then this term will be removed from the model. If significant at the 10% level results will be presented both including and excluding this term and the nature of the interaction will be investigated before deciding on an approach for presenting results that include the treatment by baseline interaction.

All available data will be included in the analysis. The analysis model table will be presented. The treatment comparisons (AM vs Sham, AEOM vs Sham and AM vs AEOM) at Months 2, 6 and 12 will also be presented with the estimate, standard error and 95% CI. If the treatment effect is significant at the 10% level then the treatment means will be compared using the least significant difference (LSD) method and the p-value presented. In addition, the estimated mean (i.e. Least-Squares mean) change from baseline in square root area for GA lesion with  $\pm$  SE of mean change, will be plotted over time by treatment group.

The model assumptions will be checked by evaluating the model residuals. A Shapiro-Wilks test will

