## Statistical Analysis Plan

---

be performed on the residuals; a p-value  $> 0.1$  will be considered proof of normality. If a Shapiro-Wilks p-value is  $\leq 0.1$ , the residual plots will be evaluated for symmetry. If the evaluation of residuals indicates a problem with the model assumptions, another transformation of the data will be considered.

The change from baseline in square root area for GA lesion will be summarized by treatment group and visit for the MITT population using the observed data and replacing missing values with predicted values from the model. Summaries will present the descriptive statistics for baseline, absolute values and change from baseline data. The absolute values for missing data will be derived as the predicted change from baseline in square root area for GA lesion plus observed baseline value.

The observed values for the square root area for GA lesion will be summarized by treatment group and visit for the MITT population. Summaries will present the descriptive statistics for baseline, absolute values and change from baseline data. The observed mean change from baseline in square root area for GA lesion with  $\pm$  SE of mean change, will be plotted over time by treatment group.

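### One by-visit summary of the primary endpoint counts model predictions as observations, so it overstates n and understates the SD of lesion growth; only that descriptive table is affected

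*SAP*

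**What the plan says.** SAP 8.1 plans two by-visit summaries of the primary endpoint in the MITT population.

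- **Filled summary.** Change in square root GA area is summarised "using the observed data and replacing missing values with predicted values from the model". Absolute values for the gaps are "derived as the predicted change from baseline in square root area for GA lesion plus observed baseline value". The content is stated as follows: "Summaries will present the descriptive statistics for baseline, absolute values and change from baseline data".
- **Observed summary.** The next paragraph adds: "The observed values for the square root area for GA lesion will be summarized by treatment group and visit for the MITT population". It comes with a plot of observed means and their SEs.

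SAP 6.1 defines the statistics: "Continuous variables will be summarized using the number of non-missing observations (n), mean, standard deviation (SD), median, minimum, and maximum". Neither section mentions a residual draw, multiple imputation, a corrected SD or a count of filled values for the filled summary. Neither says whether a prediction is the fitted group mean (given baseline) or is also conditional on the subject's own earlier visits.

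Inference comes from elsewhere in SAP 8.1, namely the MMRM fitted to the available data: "An unstructured covariance structure will be used to model the within subject error". That model supplies the treatment differences, SEs, 95% CIs and the LS-mean plot.

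**The concern.** Filling each gap with one model prediction is single conditional-mean imputation. The filled points lie on the fitted surface and lack the scatter of real measurements around it. An ordinary SD over real and filled points together is therefore too small. The n also rises, because every MITT subject now has a value at every visit. The observed-only summary would show a different n and SD for the same endpoint, and nothing in the SAP text tells a reader which SD is artificially low.

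At stake is one reported measure of spread for the primary endpoint. The trial's test result is not at stake. The growth SD is nevertheless a figure to which the design is sensitive: SAP 13, item 5, records the discrepancy between 0.21 and 0.2 mm/year, a gap of about 5%.

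**Working it through.** **Inputs from the documents**

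- Growth SD: SAP 3.3 uses "0.2mm/year and a 2-sided test at the 10% level of significance". Protocol 11.3.1 says "the standard deviation of annual square root area growth is 0.21mm/year".
- Loss to follow-up: 15-20% (Protocol 11.3.4), with 16.5% used in the inflation.
- Size: 240 randomised, 80 per analysis group after pooling sham; 67 per group evaluable.

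**Assumptions**

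- The share m missing at Month 12 within MITT equals the planned loss.
- R², the share of within-group variance that the prediction explains, is not given. I use 0, 0.5 and 0.7. For group-level predictions, R² near 0 fits Protocol 11.2.3.2, which takes square root growth to be independent of baseline size.

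**Step 1. Reproduce the plan's figures that use the SD.** One-way ANOVA, three groups of 67, df 2 and 198, alpha 0.10, noncentrality = n·Σ(μᵢ − μ̄)²/σ².

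- Means 0.23, 0.23, 0.33 with σ = 0.20: 67 × 0.006667/0.04 = 11.17, power 91.4% (stated 91%). The second scenario has the same noncentrality and power.
- Means 0.23, 0.28, 0.33: 67 × 0.005/0.04 = 8.375, power 82.6% (stated 83%).
- With σ = 0.21 the powers are 88.8%, 88.8% and 79.0%, which do not match. I therefore use 0.20 below.
- Recruitment: 201/0.835 = 240.7 (stated 240).

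**Step 2. SD of the filled change values.** A share 1 − m has variance σ² and a share m has variance R²σ². If missingness does not shift the mean,

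SD(filled) = σ·√[(1 − m) + m·R²] = σ·√[1 − m(1 − R²)].

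| R² | m = 15% | m = 16.5% | m = 20% |
|---|---|---|---|
| 0 | 0.922 (0.184 mm) | 0.914 (0.183 mm) | 0.894 (0.179 mm) |
| 0.5 | 0.962 (0.192 mm) | 0.958 (0.192 mm) | 0.949 (0.190 mm) |
| 0.7 | 0.977 (0.195 mm) | 0.975 (0.195 mm) | 0.970 (0.194 mm) |

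Entries are the ratio to the true SD and, in brackets, the SD shown when the truth is 0.20 mm. If only 8% are missing, the ratios are √0.92 = 0.959 (R² = 0) and √0.96 = 0.980 (R² = 0.5), so the SD is 2-4% too small.

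**Step 3. Simulation check.** Three visits, 80 subjects, Month 12 SD 0.20 mm, assumed correlations between adjacent visits of 0.5 to 0.85, 15-20% missing, with dropout either completely at random or dependent on Month 6 growth. Ratios to the full-data SD:

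- group-level filling: 0.86-0.92;
- subject-specific filling: 0.92-0.98;
- observed data only: about 1.00 with random dropout, 0.975-0.993 with growth-dependent dropout.

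**Step 4. Absolute values.** With an assumed baseline SD s of 0.5-0.8 mm, baseline unrelated to growth, and R² = 0, the ratio is √[s² + 0.04(1 − m)]/√[s² + 0.04]. This gives 0.986-0.996, a shrinkage of 0.4-1.4%.

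**Step 5. An SE computed by hand from the table.** At 16.5% missing, SD/√80 is 0.0204 (R² = 0) or 0.0214 (R² = 0.5), against 0.20/√66.8 = 0.0245 from observed data. That is about 17% or 13% too small. The SAP plans no such SE.

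**The case against.** The strongest reply is that nothing inferential uses this table. It reports descriptive statistics only. The two plots with SE bars use MMRM LS means and observed means. The observed summary stands beside it, and SAP 6.2 keeps original data in the listings. All of this stands.

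A reader might infer that the primary endpoint is shown with wrong error bars. The documents do not support that, because no SE, CI or error bar is planned from the filled values. The shortfall in Step 5 arises only if someone computes SD/√n from the table.

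A reader might also infer that Phase III would be sized on this SD. A sample size proportional to SD² would then be short by m(1 − R²), or 7.5-10% at R² = 0.5. However, Protocol 11.6 ties Phase III planning to the one-year analysis and names no table, and the observed SD is also reported. Such reuse is possible but undocumented.

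The size is also open to challenge. MITT requires a lesion measurement at or after Month 2 (SAP 5.5), and subjects who stop treatment may stay for assessments (Protocol 8.1), so fewer than 15-20% may be missing. R² is assumed. With strong correlation between visits and growth-dependent dropout, the simulated observed-only SD is almost as low as the subject-specific filled one (0.979 against 0.978 at 15% missing).

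The table shells are not in the supplied text, so whether they label filled values cannot be determined. A label would tell readers what was done but would not correct the SD.

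**Conclusion.** The point holds as a low-severity error in one descriptive table. Following the SAP as written, and with filled values counted as non-missing, the table overstates n and understates the SD of change wherever data are missing and the model holds. At 15-20% missing at Month 12 the SD is about 4-5% too small with subject-specific predictions (assumed R² = 0.5) and 8-11% too small with group-level predictions. The shrinkage is smaller if fewer values are missing, as may be so at Months 2 and 6. It would be larger at Month 18, where SAP 8 repeats the by-visit summaries, if more are missing there. Absolute values are affected by roughly 1% or less on the baseline SDs assumed.

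The MMRM results, both plots, the observed-only summary, the power and the sample size are unaffected.

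**What to change.** Either of two changes to SAP 8.1 is enough:

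- delete the filled by-visit summary; or
- keep it, drop the SD, and show the number of filled values in each cell. It would also help to state whether predictions are group-level or conditional on earlier visits.

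Take the spread from the observed-data summary, and precision from the MMRM LS means with their SEs and the treatment differences with their CIs, all already planned. Apply the same rule to the Month 18 repeat.

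The cost is one table or one column. Little is lost, because the LS means already give a mean that allows for missing data. The observed SD may itself be slightly low if dropout depends on growth (by at most 2.5% in the simulation above). If a spread for the full MITT set is wanted, a model-based SD or multiple imputation with residual draws would supply it, at the price of more programming.

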### **8.1.1. Sensitivity Analyses of the Primary Endpoint**

The robustness of the primary analysis will be evaluated by repeating the primary analysis with the per-protocol population.

In addition, the following sensitivity analyses will be conducted using the MITT population:

- A MMRM analysis including only data which is within a specific time period of the last injection. Month 6 data will be included if a subject was dosed on or after Month 4, and Month 12 will be included if a subject was dosed on or after Month 8. All Month 2 data will be included, as the criteria to be included in the MITT population requires a subject to have had at least one dose of study medication. The primary analysis will be repeated using this subset of data.
- An analysis using an LOCF method for handling missing data as specified in Section 6.2.1. All available Month 12 data will be included and missing data will be replaced using LOCF method. An analysis of Covariance (ANCOVA) model will be fitted for the Month 12 change from baseline in square root area for GA lesion, that includes baseline as a covariate and treatment (3 groups: AM, AEOM and Sham).
- Completer analysis i.e. observed data for those subjects who complete the treatment period (for subjects receiving monthly injections this will be 12 injections and for subjects receiving EOM injections this will be 6 injections) and have their Month 12 assessment. The analysis model will be the same as for the primary analysis.

For each approach, a summary over time will be presented. The analysis model table will be presented. The treatment comparisons (AM vs Sham, AEOM vs Sham and AM vs AEOM) will also be presented with the estimate, standard error and 95% CI. If the treatment effect is significant at

## Statistical Analysis Plan

---

the 10% level then the treatment means will be compared using the least significant difference (LSD) method and the p-value presented.

### **8.1.2. Additional Analyses of the Primary Endpoint**

The completer cases at Month 6 i.e. observed data for those subjects who complete 6 months of treatment (for subjects receiving monthly injections this will be 6 injections and for subjects receiving EOM injections this will be 3 injections) and have their Month 6 assessment; will be analysed using the same model as the primary analysis. This analysis will be repeated for the completer cases at Month 18 i.e. subjects who complete the treatment period (for subjects receiving monthly injections this will be 13 injections and for subjects receiving EOM injections this will be 7 injections) and have their Month 18 assessment.

The untransformed change from baseline in area for GA lesion at Month 2, 6 and 12 will be analysed for the MITT population using the same model as the primary analysis. The estimated mean change from baseline in area for GA lesion with  $\pm$  SE of mean change, will also be plotted over time by treatment group.

Additional summaries and analyses will be performed for the subgroups detailed in Section 6.4. These analyses will be based on the MITT population and will use the same analysis approach as specified in Section 8.1, however the treatment by baseline interaction will only be investigated if it is significant for the primary analysis.

In addition, the observed mean change from baseline in square root area for GA lesion  $\pm$  SE of mean change, will be plotted over time by treatment group and reticular pseudodrusen at baseline (present/absent) on the same plot.

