13. Participation in another interventional clinical study, or use of any experimental treatment for AMD or any other investigational new drug within 6 weeks or 5 half-lives of the active (whichever is longer) prior to the start of study treatment. Note: clinical trials solely involving observation, over-the-counter vitamins, supplements, or diets are not exclusionary.
14. Medical or psychiatric conditions that, in the opinion of the investigator, make consistent follow-up over the treatment period unlikely, or in general a poor medical risk because of other systemic diseases or active uncontrolled infections.

15. Any screening laboratory value (hematology, serum chemistry or urinalysis) that in the opinion of the Investigator is clinically significant and not suitable for study participation.

16. Hypersensitivity to fluorescein.

Endpoints

The primary endpoints are to demonstrate superiority of monthly and every-other-month (EOM) APL-2 IVT injections compared to sham injections based upon the mean change in GA lesion size as measured by FAF and the number and severity of treatment emergent adverse events (TEAEs).

Primary Efficacy Endpoint

- The primary endpoint is the change in square root geographic atrophy (GA) lesion size from baseline to Month 12 as measured by FAF.

Primary Safety Endpoint

- Number and severity of local and systemic treatment emergent adverse events (TEAE).

Secondary Endpoints

- Secondary Efficacy Endpoints

- Mean change in GA lesion size as measured by SD-OCT.
- Change in best-corrected visual acuity (BCVA).
- Change in low luminance best-corrected visual acuity (LL-BCVA).
- Relationship between GA lesion size changes and changes in BCVA.
- Relationship between LL-BCVA and low luminance deficit with GA lesion size changes.
- Changes in distance of GA lesion from fovea (foveal encroachment).
- Change in drusen size over time.
- Relationship between GA lesion size changes and presence of reticular pseudodrusen.
- Relationship between genetic polymorphisms associated with AMD with GA progression and response to APL-2.
- Comparison of incidences of new onset macular neovascularization (MNV) between the treatment and sham arms.

- Secondary Safety Endpoints

- Changes in vital signs.

- Increase in intraocular pressure (IOP).
- Infectious endophthalmitis (defined as treatment for infectious endophthalmitis) or non-infectious endophthalmitis.
- Ocular inflammation.
- Retinal detachment or tear.
- Vitreous hemorrhage.

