### **4.2.8. Genetic Polymorphisms**

Genetic marker analysis will be performed on blood samples collected at Month 2 for all subjects at selected sites where genetic testing is allowed. The prioritized genes, C3, CFI, CFH, CFB, C2, ARMS2/HTRA1, will be explored to assess whether they are prognostic/predictive factors of the growth in GA area and the APL-2 treatment. For the prioritized genes the following SNPs, that have been highly associated with AMD, will be investigated:

- CFH: rs1061170, rs1410996, rs10737680, rs1048663
- CFB: rs438999, rs541862, rs4151667, rs641153
- C2: rs9332739

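### Subgroup analyses of the primary endpoint plan no treatment-by-subgroup contrast (continuous baseline lesion size aside), and separate stratum p-values do not show whether the effect differs.

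*SAP*

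**What the plan says.** SAP 8.1.2 says "Additional summaries and analyses will be performed for the subgroups detailed in Section 6.4", and that these analyses "will use the same analysis approach as specified in Section 8.1", in the MITT population. SAP 6.4 lists eight factors: country (3 levels), reticular pseudodrusen (2), age (3), low-luminance deficit (2), fellow-eye CNV (2), GA laterality (2), lesion size (2) and sex (2). That makes 18 strata.

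The Section 8.1 MMRM has treatment, baseline and visit, and the interactions "treatment by visit interaction, visit by baseline interaction and treatment by baseline interaction". Subgroup appears neither as a main effect nor in an interaction. The only interaction that 8.1.2 mentions for the subgroup runs is with baseline lesion size: "the treatment by baseline interaction will only be investigated if it is significant for the primary analysis".

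On testing, SAP 6.1 says "All statistical tests will be 2-sided at the 0.1 level of significance" and rules out multiplicity adjustment. Section 8.1 tests the overall treatment effect at 10% and, if it is significant, gives LSD p-values for the pairs. It also gives an estimate, standard error and 95% CI for each treatment comparison.

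Three other items come close to a comparison between strata, but none formally compares treatment effects across the levels of a listed subgroup factor:
- the descriptive plot by treatment and pseudodrusen status (SAP 8.1.2);
- the neovascularization comparison repeated by fellow-eye CNV (SAP 8.2.2);
- the primary model's treatment-by-baseline test, which addresses lesion size only, on the continuous scale.

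**The concern.** A subgroup analysis is read for one question: is the effect larger in some patients than in others? A set of within-stratum tests does not answer it. Each test asks whether the effect in that stratum is distinguishable from zero, and the answer depends heavily on stratum size. A significant result in one level beside a non-significant result in the other is easily taken as a difference in effect, although it is a common outcome when the effect is the same in both.

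The trial is meant to support Phase III (Protocol 5.1), and Phase III planning rests on the one-year analysis (Protocol 11.6). The rationale in Protocol 4.2.1 itself cites a biomarker-defined subpopulation result from another complement inhibitor's Phase II study. If strata are used to shape a later population, the choice could follow a chance pattern.

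**Working it through.** **Inputs.** Design effect 0.33 − 0.23 = 0.10 mm (Protocol 11.3.3). SD 0.21 (Protocol 11.3.1) or 0.20 (SAP 3.3; SAP Section 13, item 5, says that 0.20 was used for the power table). 67 evaluable per group after pooling the shams. Two-sided alpha 0.10. The documents give no stratum sizes, so the splits 50/50, 33/67 and 20/80 are assumptions. Like the protocol's own power table, the calculation uses a one-way ANOVA on the 12-month change as a stand-in for the MMRM.

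**1. The plan's own figure.** Noncentrality λ = n × Σ(μ − mean)² / SD².
- Means 0.23, 0.23, 0.33: the sum of squares is 0.006667, so λ = 67 × 0.006667 / 0.04 = 11.17 and power is 91.4%. The second scenario has the same λ.
- Means 0.23, 0.28, 0.33: λ = 67 × 0.005 / 0.04 = 8.375 and power is 82.6%.

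The protocol states 91%, 91% and 83%, so the table reproduces at SD 0.20. At SD 0.21 the values are 88.8%, 88.8% and 79.0%.

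**2. Power within a stratum**, with the full 0.10 mm effect in both active arms (overall 10% test):

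| Share of sample | SD 0.20 | SD 0.21 |
|---|---|---|
| one half (33.5 per group) | 66% | 62% |
| one third | 50% | 47% |
| one fifth | 35% | 32% |

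A normal approximation for one active arm against sham in a half, with n rounded down to 33, agrees: Φ(0.10 / (SD × √(2/33)) − 1.645) = 65% and 61%.

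**3. Chance of a split verdict when the effect is identical in both levels.** With stratum powers p₁ and p₂ this is p₁(1 − p₂) + p₂(1 − p₁).
- 50/50, SD 0.20: 2 × 0.663 × 0.337 = 45%. SD 0.21: 2 × 0.624 × 0.376 = 47%.
- 33/67, SD 0.20: 0.500 × 0.218 + 0.782 × 0.500 = 50%.
- 20/80, SD 0.20: 0.346 × 0.153 + 0.847 × 0.654 = 61%.

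Across all eight factors, a simulation of 2,000 trials (201 subjects, SD 0.20, factors independent of each other, levels equal in size, uniform effect) gave at least one factor with a split verdict in 96% of trials.

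**4. No effect anywhere.** 18 × 0.10 = 1.8 false-positive strata are expected. The chance of at least one is 1 − 0.9¹⁸ = 85% if the tests were independent. They are not, because the factors divide the same subjects; the simulation gave about 66%.

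**5. What an interaction test would deliver.** For one active arm against sham, with n₁ and n₂ per arm in the two levels, SE = SD × √(2/n₁ + 2/n₂).
- 50/50, SD 0.20: SE = 0.20 × √(4/33.5) = 0.069. The 95% CI half-width is 1.96 × 0.069, about 0.14 mm.
- If the whole 0.10 mm lies in one level and none in the other, power at 10% is 42% (50/50), 39% (33/67) or 32% (20/80). At SD 0.21 it is 40%, 37% and 30%.
- The difference in effect detectable with 80% power is (1.645 + 0.842) × SE, which is 0.17 to 0.22 mm at SD 0.20. That exceeds the whole design effect.
- Eight such tests at 10% give 8 × 0.10 = 0.8 expected false positives, and 1 − 0.9⁸ = 57% for at least one if independent.

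**The case against.** Several points on the other side have force.

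- **Separate fitting is an inference.** SAP 8.1.2 does not say that the model is run inside each stratum. It remains the natural reading, because a model with no subgroup term cannot otherwise yield subgroup results. The SAP's index of tables was not in the text reviewed, so the planned outputs could not be checked there.
- **The plan is not silent on size of effect.** Each comparison comes with an estimate, standard error and 95% CI, so a reader could difference two levels by hand. For lesion size, the treatment-by-baseline test already looks at effect modification. It would be too strong to infer that the subgroup analyses cannot show a difference at all; the gap is that the plan does not make the comparison.
- **These are additional analyses in a Phase II trial.** No section says that subgroups will choose the Phase III population. That consequence is a possibility, not a stated plan.
- **The interaction is weakly powered**, and eight such tests bring their own false positives. This stands and limits what the fix can promise.
- **SAP 4.1 and 8.1.3 show that the 12-month results had been reviewed** before this version. A new Month 12 model is therefore post hoc.

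Two stronger readings are tempting. One is that the protocol's pseudodrusen endpoint, "Relationship between GA lesion size changes and presence of reticular pseudodrusen", demands an interaction. As worded it is an association with growth, so it does not, although a pooled model would estimate that association as well. The other is that the unadjusted 10% rule covers the listed SNPs. SAP 4.2.8 says that the genes "will be explored to assess whether they are prognostic/predictive factors of the growth in GA area", but SAP 2.1 and 8.2.8 place the genetic analyses with a separate institute and in a separate report. Its tests and any multiplicity control are not in these documents, so no error rate for the SNPs can be asserted.

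**Conclusion.** The point holds as a gap in a supportive analysis. Seven of the eight factors have no planned assessment of whether the treatment effect differs between levels. The eighth, lesion size, has one only through the continuous baseline term in the primary model. Within-stratum significance is a poor substitute: under an identical 0.10 mm effect, a split verdict is expected in about 45 to 47% of trials for equal halves, and more often for unequal ones.

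These figures rest on the design effect, SD 0.20 to 0.21, 67 per group and assumed stratum shares. Only the low-luminance deficit factor, cut at its median, is close to half and half by design. The MMRM's use of baseline and earlier visits could shift the numbers somewhat, but not the logic. The primary analysis and its conclusion are not affected.

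**What to change.** For each factor in SAP 6.4, replace the stratum fits with one MMRM on the full MITT population. Keep the Section 8.1 terms and add subgroup, subgroup-by-visit, treatment-by-subgroup and treatment-by-subgroup-by-visit. From that model report:

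- the interaction estimate with its 95% CI at Month 12, and at Month 18 for the final analysis, for each active arm against pooled sham;
- the within-stratum treatment estimates with CIs beside it.

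State that within-stratum significance will not be used to claim that effects differ. Label all of this exploratory, and label the Month 12 results post hoc because the 12-month data had already been reviewed.

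The cost is programming: eight pooled models in place of 18 stratum fits. The limits should be stated with the results: interaction power of about 30 to 42% even if the whole 0.10 mm effect lies in one level, and 0.8 expected false positives over eight tests at 10%. Interpretation should therefore rest on the interaction estimate and its CI. A non-significant interaction should not be read as proof that the effect is uniform.
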